5.5 Concomitant Treatments

5.5.1 Prohibited treatments

- Other anti-tumor therapy (except for palliative radiotherapy), chemotherapy, immunotherapy, targeted therapy, or hormone therapy.
- Immunosuppressants and high-dose glucocorticoids (except for treatments of AEs at a dose of no more than 10 mg daily prednisone or equivalents).
 - Immunoglobulins.
 - Live attenuated vaccine.
 - Autologous hematopoietic stem cell transplantation.

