Appendix 7: IBI308 Administration Adjustments and Toxicity Management

Table 1. IBI308 administration adjustments and toxicity management of major potential irAEs

	AE Grade/Administration Adjustments		Toxicity Management
General Principles	AEs are graded according to NCI CTCAE v4.03. Refer to this guideline if the event is an irAE		
It is recommended to manage irAEs according to the guideline in this table.
 
 - Subjects shall be fully evaluated to rule out any alternative causes (e.g. PD, concomitant medication, infection, etc.) - The event is an irAE if there are no clear alternative causes and treatment with corticosteroids is required - Consider symptomatic and local treatment for low grade events (grade 1 or 2, unless otherwise stated) - Consider systemic glucocorticoid therapy for persistent low grade events (grades 1–2) or severe events (grade \geq 3) - If the event re-occurs or worsens during tapering of glucocorticoids, the glucocorticoid dose shall be increased until symptoms resolve
	Grade 1	No dose adjustments required	
	Grade 2	Interrupt 
 • If worsens, treat as a grade 3/4 event • If reduces to grades 0–1 or baseline, continue the treatment at the next scheduled date 	
	Grade 3	Interrupt or permanently discontinue	

	AE Grade/Administration Adjustments		Toxicity Management
	Grade 4	Permanently discontinue	
or improve, then taper with a lower rate
 
 - Once persistent clinical improvement is observed, subjects receiving glucocorticoids IV can start tapering the dose or switch to an equivalent dose of glucocorticoid PO at an earlier time (a lower bioavailability of oral administration should be considered) - For events that unresponsive to glucocorticoid treatment, consider a stronger immunosuppressants, e.g. TNF blockers (e.g. infliximab) or mycophenolate mofetil, after discussing with the physicians - For grade 3/4 local inflammation of lesions (such as local pain, irritation, and rash), IBI308 may be continued as determined by the investigator

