Pneumonitis	Any grade		
 - Monitor signs and symptoms of pneumonitis or interstitial lung disease (e.g. new shortness of breath, cough, chest pain or exacerbation of existing symptoms and signs), evaluate subjects by imaging, pulmonary function, and other examinations - Initial examination may include clinical evaluation, arterial oxygen saturation, laboratory tests, and high-resolution CT scans
	Grade 1	No dose adjustments required However, consider interrupting the treatment based on clinical needs and during diagnostic tests for other causes	
For grade 1 events:
 
 - Monitor signs and symptoms and arterial oxygen saturation for 2–4 days - Perform other laboratory tests if clinically indicated - Consider consulting a respirologist and infectious diseases specialist

	AE Grade/Administration Adjustments		Toxicity Management
	Grade 2	Interrupt 
 • If worsens, treat as a grade 3/4 event • If reduces to grades 0–1 or baseline, continue the treatment at the next scheduled date 	For grade 2 events: 
 – Monitor signs and symptoms daily, consider hospitalization – Discuss with sponsor's medical manager, consider systemic glucocorticoid treatment – Repeat imaging if clinically indicated – If no improvement is seen within 3–5 days, consider other tests and increasing the glucocorticoid dose – If no improvement is seen within 3–5 days, consider a stronger immunosuppressant (e.g. infliximab) – Once improved, taper glucocorticoids within 4 weeks, and consider prophylactic antibiotic – Consider consulting a respirologist and infectious diseases specialist

	AE Grade/Administration Adjustments		Toxicity Management
	Grade 3 or grade 4	Permanently discontinue	
For grade 3–4 events:
 
 - Discuss with sponsor's medical manager - Consider consulting a respirologist and infectious diseases specialist - Hospitalization - Supportive care (oxygen) - Begin systemic glucocorticoid treatment based on experience - If no improvement is seen within 3–5 days, consider other tests and stronger immunosuppressants (e.g. infliximab) - Once improved, taper glucocorticoids within 4 weeks, and consider prophylactic antibiotic

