Diarrhea or Enterocolitis	Any grade		
 - Monitor possible signs and symptoms related to diarrhea/enterocolitis (abdominal pain, enterospasm, changes in bowel habits, melena, mucous stool, bloody stool, or muscle guarding) - Subjects shall be fully evaluated to rule out any alternative causes (e.g. PD, infection, etc.) - If alternative causes cannot be determined, consider glucocorticoid treatment for low grade events to prevent from escalating to high grade - Use analgesics with caution (may mask the symptoms of perforation and peritonitis)

	AE Grade/Administration Adjustments		Toxicity Management
	Grade 1	No dose adjustments required	
For grade 1 events:
 
 - Closely monitor symptom exacerbation - Consider symptomatic treatment, including fluid replacement, electrolyte replacement, diet modifications, and loperamide administration
	Grade 2 or Grade 3	
Interrupt
 
 • If worsens, treat as a grade 3/4 event • If reduces to grades 0–1 or baseline, continue the treatment at the next scheduled date 	
For grade 2–3 events:
 
 - Consider symptomatic treatment, including fluid replacement, electrolyte replacement, diet modifications, and loperamide and/or budesonide administration - If the event persists for > 3–5 days or worsens, consider systemic corticosteroid treatment - If no improvement is seen within 3–5 days, consider other tests and increasing the glucocorticoid dose - If no improvement is seen or exacerbation occurs within 3–5 days, consider other tests and stronger immunosuppressants (e.g. infliximab) - If not reduces to grade 0–1 within 3–4 days, discuss with sponsor's medical manager - Once improved, taper glucocorticoids within 4 weeks, and consider prophylactic antibiotic

	AE Grade/Administration Adjustments		Toxicity Management

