	Grade 2	Interrupt 
 • If worsens, treat as a grade 3/4 event • If reduces to grades 0–1 or baseline, continue the treatment at the next scheduled date 	For grade 2 events: 
 – If not reduces to grade 0–1 within 3–4 days, discuss with sponsor's medical manager – For ALT, AST, or TBIL elevations, retest hepatic function within 3–4 days and increase monitoring frequency – If the event persists for > 3–5 days or worsens, consider systemic corticosteroid treatment – If no improvement is seen within 3–5 days, consider other tests and increasing the glucocorticoid dose – If no improvement is seen within 3–5 days, consider stronger immunosuppressants (e.g. mycophenolate mofetil) – Once improved, taper steroids within 4 weeks, and consider prophylactic antibiotic

	AE Grade/Administration Adjustments		Toxicity Management
	Grade 3 or grade 4	Permanently discontinue	
For grade 3–4 events:
 
 - Discuss with sponsor's medical manager - Begin systemic glucocorticoid treatment based on experience - If no improvement is seen within 3–5 days, consider stronger immunosuppressants (e.g. mycophenolate mofetil) - If no improvement is seen within 3–5 days, consider other immunosuppressants based on local guidelines - If applicable, consult a gastroenterologist, perform abdominal examination and imaging - Once improved, taper glucocorticoids within 4 weeks, and consider prophylactic antibiotic
Dermatitis	Any grade		
 - Monitor signs and symptoms of dermatitis, e.g. rash, exudation, hypopigmentation, photosthesia, and pruritus - If there is formation of bullae, contact the sponsor's medical manager - Consult a dermatologist - Perform skin biopsy when necessary
	Grade 1	No dose adjustments required	
For grade 1 events:
 
 - Consider symptomatic treatment, including oral antipruritic agents (e.g. diphenhydramine or hydroxyzine) and local treatment (e.g. urea cream or topical glucocorticoids)

	AE Grade/Administration Adjustments		Toxicity Management

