Immune-related neurotoxicities (except for myasthenia gravis and Guillain-Barrésyndrome)	Any grade		
 - Monitor the subject's systemic symptoms (headache, nausea, dizziness, behavioral changes, or weakness) - Subjects shall be fully evaluated to rule out any alternative causes (e.g. PD, infection, metabolic syndrome, medications, etc.) - Consider appropriate diagnostic tests (e.g. electromyography and nerve conduction study) - If applicable, begin symptomatic treatment and consult a neurologist
	Grade 1	No dose adjustments required	- Closely monitor signs and symptoms
	Grade 2	Interrupt 
 • If reduces to grades 0–1 or baseline, continue the treatment at the next scheduled date • If worsens, treat as a grade 3 event 	For grade 2–4 events: 
 - Discuss with sponsor's medical manager - Consider consulting a nephrologist - Hospitalization when necessary - Manage neuropathy and neuropathic pain with appropriate medications (e.g. gabapentin, duloxetine, etc) - Consider systemic corticosteroid treatment
	Grade 3	Permanently discontinue	
 - If no improvement is seen within 3–5 days, consider other tests and immunosuppressants (e.g. intravenous immunoglobulin G, IVIgG) - Once stabilized, taper glucocorticoids within \geq 4 weeks
	Grade 4		

	AE Grade/Administration Adjustments		Toxicity Management

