Immune-related peripheral neuropathy, e.g. Guillain-Barré syndrome and myasthenia gravis	Any grade		
 - Monitor signs and symptoms closely (myasthenia gravis: eye or limb soreness and discomfort, blurred vision, fatigue, which worsens as the day goes on; Guillain-Barrésyndrome: sudden and severe nerve pain, paralysis of the limbs, and prickling or burning sensation in the limbs) - Timely diagnosis of immune-related peripheral neuropathy is very important, as subjects may suffer from unpredictable acute compensation, which may lead to severe disease or death. Pay special attention to signs and symptoms that may indicate serious consequences, e.g. significant dysphagia, rapidly progressive weakness, respiratory insufficiency, or autonomic dysfunction - Neuroelectrophysiological tests shall be performed to rule out any alternative causes (e.g. PD, infection, metabolic syndrome, medications, etc.) It is worth noting that cancer itself and cancer treatment can affect neural function. The diagnosis of immune-related peripheral neuropathies is thus difficult. Neurological consultation shall be actively carried out. - Plasmapheresis or IVIgG should be considered for subjects with Guillain-Barrésyndrome (glucocorticoids are generally ineffective)
	Grade 1	No dose adjustments required	
For grade 1 events:
 
 - Discuss with a physician - Monitor signs and symptoms - Consider consulting a nephrologist

	AE Grade/Administration Adjustments		Toxicity Management
	Grade 2	Interrupt 
 • If reduces to grades 0–1 or baseline, continue the treatment at the next scheduled date • If worsens, treat as a grade 3–4 event 	For grade 2–4 events: 
 – Discuss with sponsor's medical manager – Monitor signs and symptoms – Consider consulting a nephrologist – Hospitalization when necessary – Manage neuropathy and neuropathic pain with appropriate medications (e.g. gabapentin, duloxetine, etc.)

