	Grade 3 or grade 4	Permanently discontinue	
Myasthenia Gravis
 
 – Glucocorticoids may be used to treat myasthenia gravis (shall be used under the supervision of a neurologist since corticosteroids, especially high-dose, may result in initial exacerbation of symptoms) – Subjects intolerant to glucocorticoids may be treated with plasmapheresis or IVIgG – For myasthenia gravis-like neurotoxicities, consider acetylcholinesterase inhibitors in addition to glucocorticoids 
Guillain-Barre Syndrome
 
 – Plasmapheresis or IVIgG should be considered for subjects with Guillain-Barré syndrome (glucocorticoids are generally ineffective)

Table 2. IBI308 administration adjustments and toxicity management of other potential irAEs

	CTD Grade/Administration Adjustments	Toxicity Management
Any grade	Dose adjustments are not required for AEs unrelated to study treatment or laboratory abnormalities that are not clinically significant (events caused by underlying disease)	Manage based on local clinical practice
Grade 1	No dose adjustments required	
Grade 2	Consider interruption until reduces to grade 0–1 or baseline	
Grade 3	
 • First occurrence: interrupt until reduces to grade 0–1 or baseline • Second occurrence: permanently discontinue • For an AE that reduces to grades 0–2 within 7 days, or grades 0–1 or baseline within 14 days, interrupt and then resume the treatment at the next scheduled date Otherwise, permanently discontinue 	
Grade 4	Permanently discontinue (Note: for grade 4 laboratory abnormalities, the event shall be determined based on clinical signs/symptoms and the clinical judgment of the investigator)	

Table 3. Dose adjustments and toxicity management for infusion reactions

CTD Grade	Administration Adjustments	Toxicity Management
Any grade		
 - Manage based on local clinical practice - Monitor infusion-related reactions (e.g. fever or chills, flushing and/or pruritus, changes in heart rate and blood pressure, dyspnea, chest discomfort, rash, etc.) and allergic reactions (e.g. systemic urticaria, angioedema, asthma, hypotension, tachycardia, etc.)

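### Protocol 5.5.1 bans immunoglobulins, and on its plain reading immunosuppressants, that Appendix 7 tells sites to consider for immune-related events; add an exemption and settle PPS status in advance

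*Protocol*

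**What the plan says.** **The prohibition.** Protocol 5.5.1 lists as prohibited "Immunosuppressants and high-dose glucocorticoids (except for treatments of AEs at a dose of no more than 10 mg daily prednisone or equivalents"). The only adverse-event exception on that line carries a prednisone-equivalent cap. Immunoglobulins have their own line, with no exception.

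**The toxicity guidance.** Protocol 5.4 ties the diagnosis of a non-endocrine irAE to a need for glucocorticoids or other immunosuppressants, and refers to Appendix 7. Appendix 7, Table 1 then offers:

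- General principles, for events that do not respond to glucocorticoids: "consider a stronger immunosuppressants, e.g. TNF blockers (e.g. infliximab) or mycophenolate mofetil, after discussing with the physicians".
- Pneumonitis, grade 2: "consider a stronger immunosuppressant (e.g. infliximab").
- Diarrhea or enterocolitis, grade 2–3: "consider other tests and stronger immunosuppressants (e.g. infliximab").
- Hepatitis, grade 2: "consider stronger immunosuppressants (e.g. mycophenolate mofetil").
- Neurotoxicity, grade 2–4: "consider other tests and immunosuppressants (e.g. intravenous immunoglobulin G, IVIgG").
- Guillain-Barré syndrome, any grade: "Plasmapheresis or IVIgG should be considered for subjects with" that condition.
- Myasthenia gravis: "Subjects intolerant to glucocorticoids may be treated with plasmapheresis or IVIgG".

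**The per-protocol set.** Protocol 8.3 and SAP 3.1 leave users of prohibited medication out of the PPS. SAP 3.2 lists such use as a major deviation, to be reviewed before database lock. None of the three mentions irAE treatment. The FAS definition has no concomitant-medication criterion.

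**The concern.** The same agents are prohibited in one section and suggested in another, and no sentence says which prevails. A site with a grade 2 pneumonitis that is not improving on glucocorticoids can follow Appendix 7 and breach the plain wording of 5.5.1, or follow 5.5.1 and forgo an Appendix 7 option. Toxicity instructions should not leave that open. The protocol expects irAEs (section 7.8.1), so the situation is foreseeable.

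The statistical stake is secondary. If Appendix 7 treatment counts as prohibited medication, PPS membership depends partly on a toxic effect of the drug. The question would then be settled at the pre-lock review, in an open-label single-arm trial where responses can be known.

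**Working it through.** No figure in the plan is in dispute. The check sets the texts side by side and then bounds the PPS effect.

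**1. Is each Appendix 7 agent caught by 5.5.1?**

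| Agent | Appendix 7 | Protocol 5.5.1 | Conflict |
|---|---|---|---|
| Intravenous immunoglobulin | Neurotoxicity, Guillain-Barré syndrome, myasthenia gravis | Prohibited, no exception | Certain |
| Infliximab | Pneumonitis, diarrhea/enterocolitis, general principles | Prohibited; a cap in prednisone equivalents cannot be applied to it | Likely |
| Mycophenolate mofetil | Hepatitis, general principles | As for infliximab | Likely |
| Systemic glucocorticoids | Most irAE rows, no dose given | Adverse-event use capped at 10 mg/day prednisone equivalent | Likely; rests on inference about dose |

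Topical steroids, symptomatic treatment, thyroxine and insulin are not part of the conflict.

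**2. Are the affected subjects still on study treatment?** Some are. For grade 2 pneumonitis, hepatitis, neurotoxicity and peripheral neuropathy, and for grade 2–3 diarrhea, Appendix 7 interrupts IBI308 and lets it continue at the next scheduled dose after recovery. For grades that require permanent discontinuation, 5.5.1 does not say whether the prohibition still applies.

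**3. Does another section lift the prohibition?** Not expressly. Section 5.5.2 permits medication for treatment-related adverse events, but only where it meets protocol requirements. A drug on the prohibited list does not clearly do so.

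**4. How far could the PPS estimate move?** The inputs are:

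- Base: 19 responders of 28, from the Summary of Amendment. This count takes pseudo-progression into consideration and serves only as an illustration.
- Subjects removed, *r*: 1 to 3. This is an assumption, because the documents give no count of subjects who received these agents.
- Interval: exact (Clopper-Pearson) 95%. The lower limit for *x* of *n* is the 2.5% quantile of Beta(*x*, *n* − *x* + 1).

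With no removal, 19/28 = 67.9% (47.6% to 84.1%). If all *r* removed are responders the rate is (19 − *r*)/(28 − *r*). If none are, it is 19/(28 − *r*).

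| *r* | All responders: rate (lower limit) | No responders: rate (lower limit) |
|---|---|---|
| 1 | 18/27 = 66.7% (46.0%) | 19/27 = 70.4% (49.8%) |
| 2 | 17/26 = 65.4% (44.3%) | 19/26 = 73.1% (52.2%) |
| 3 | 16/25 = 64.0% (42.5%) | 19/25 = 76.0% (54.9%) |

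Removal of responders alone brings the lower limit below 30% only at *r* = 9: 11/20 gives 31.5% at *r* = 8, and 10/19 gives 28.9%.

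**The case against.** The best reply is that the protocol, read as a whole, plainly means to allow these drugs:

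- Section 5.3.2 provides for interruptions beyond 6 weeks while glucocorticoids are reduced for irAEs, with resumption after consulting the sponsor's medical manager.
- Section 5.4 defines irAEs by the need for such treatment.
- Section 5.5.2 permits medication for treatment-related adverse events.
- Section 7.8.1 calls Appendix 7 the detailed guide.

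The exception in 5.5.1 can also be read as two alternatives: treatment of adverse events, or a dose of at most 10 mg/day. That reading gives the clause some work to do, since exclusion criterion 9 treats 10 mg/day as a physiological dose and the line concerns high doses. On it, the conflict over infliximab, mycophenolate and glucocorticoids disappears.

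This much stands: the intent is probably permissive, and the conflict over immunosuppressants and glucocorticoids is likely rather than certain. It does not rescue the immunoglobulin line, which has no exception to interpret.

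A reader might go further and infer that sites will withhold needed treatment. The documents do not support that. Appendix 7 calls for discussion with the sponsor's medical manager for grade 2 pneumonitis, for grade 2–3 diarrhea and grade 2 hepatitis that do not settle within 3–4 days, and for grade 2–4 neurotoxicity and peripheral neuropathy. A query would normally be resolved there.

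On the PPS, treatment given under the protocol's own appendix is hard to call a deviation. Equally, a sponsor could defend a PPS without subjects who received strong immunosuppressants during anti-PD-1 therapy. Both points stand. What is missing is a choice made in advance, and the documents do not dictate which choice.

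**Conclusion.** The inconsistency is real: certain for immunoglobulins, and likely for immunosuppressants and for glucocorticoids above 10 mg/day prednisone equivalent. It reaches subjects who may resume IBI308. It is a minor consistency and safety-instruction correction, worth making because it costs almost nothing.

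The PPS consequence is conditional and small. It arises only if Appendix 7 treatment is counted as prohibited medication, and its size rests on the assumed 1 to 3 removals and the illustrative 19/28. A reader might infer that the efficacy conclusion is at risk. It is not: the FAS result, type I error and sample size do not depend on this clause, and the illustrative PPS lower limit would fall below 30% only if at least 9 responders were removed. I take the PPS as supportive. SAP 5.5 names both FAS and PPS for efficacy without ranking them.

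**What to change.** In protocol 5.5.1, add to both the immunosuppressant/glucocorticoid line and the immunoglobulin line: *except when given to manage irAEs in accordance with Appendix 7*. The clinical content remains the sponsor's decision.

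In protocol 8.3 and SAP 3.1/3.2, add one sentence, settled before the deviation review, stating whether Appendix 7 treatment counts as prohibited medication for the PPS. Once 5.5.1 carries the exemption, the default is that it does not. If the sponsor prefers to exclude subjects given strong immunosuppressants, the sentence should say so and name the agents. The other PPS exclusions, such as fewer than 2 cycles or compliance below 80%, stay as they are.

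The cost is one clause on two lines of 5.5.1 and one sentence in the analysis-set text of each document, with no new data and no change to the primary analysis.

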5.5.2 Permitted treatments

- Medications that meet the protocol requirements, as determined by the investigator (e.g. concomitant medication used for disease-related symptoms and treatment-related AEs).
 - Long-term medication for underlying diseases such as high blood pressure and diabetes..
 - Supportive care for relieving tumor-related symptoms.
 - Use of topical, such as dermal, ocular, nasal, and inhaled, corticosteroids.

5.5.3 Drug-drug interactions

- IBI308: No interaction information is currently available.

5.6 Treatment Compliance

Study treatment is given at the study sites. Treatment compliance is monitored by medication dispensing and return records, medical records, and eCRFs.

5.7 Medication Return and Destruction

The packages and vials of used or partially used investigational drugs for this study shall be verified by the Clinical Research Associate (CRA) and returned to the sponsor for destruction. Arrangements for the return of investigational drug will be made by the designated CRA.

Upon the completion or discontinuation of the study, all unused or expired investigational drugs must be returned to the sponsor for destruction. Arrangements for the return of investigational drug will be made by the designated CRA.

5.8 Investigational Drug Records

The designee of the study sites shall make timely records of receiving, dispensing, using, storing, returning, and destroying the study drugs in accordance with the relevant regulations and guidelines and the operation requirements of this study.

